A non-interventional, post-authorization safety study (PASS) to evaluate long-term safety of anakinra (Kineret[®]) in patients with systemic juvenile idiopathic arthritis

EU PAS Register No: ENCEPP/SDPP/28378

Protocol version: 1.0 dated 13 Mar 2019

Confidential

This protocol contains confidential information belonging to Swedish Orphan Biovitrum. Except as may be otherwise agreed to in writing, by accepting or reviewing these materials, you agree to hold such information in confidence and not to disclose it to others (except where required by applicable law) nor use it for unauthorized purposes. In the event of actual or suspected breach of this obligation, Swedish Orphan Biovitrum should be promptly notified.

PASS information

Title	A non-interventional, post-authorization safety study (PASS) to evaluate long-term safety of anakinra (Kineret®) in patients with systemic juvenile idiopathic arthritis
Protocol version identifier	1.0
Date of last version of protocol	13 Mar 2019
EU PAS register number	ENCEPP/SDPP/28378
Active substance	Pharmacotherapeutic group: Immunosuppressants, Interleukin inhibitors, ATC code: L04AC03 anakinra
Medicinal product	Kineret® 100 mg/0.67 ml solution for injection in pre-filled syringe
Product reference	EU/1/02/203/001 - 100 mg - 1-pack EU/1/02/203/002 - 100 mg - 7-pack EU/1/02/203/003 - 100 mg - 28-pack EU/1/02/203/005 - 100 mg/0.67 ml - 1-pack EU/1/02/203/006 - 100 mg/0.67 ml - 7-pack EU/1/02/203/007 - 100 mg/0.67 ml - 28-pack
Procedure number	EMA/H/C/000363/II/0056
Marketing authorization holder(s)	Swedish Orphan Biovitrum AB (publ), SE-112 76 Stockholm, Sweden
Joint PASS	No
Research question and objectives	Evaluate and characterize long-term safety of Kineret when used in standard clinical practice to treat patients with systemic juvenile idiopathic arthritis (SJIA), including macrophage activation syndrome (MAS) as an event of special interest (ESI).
Country(-ies) of study	Secondary use of data collected in Croatia, Denmark, France, Germany, Greece, Hungary, Israel, Italy, Latvia, Netherlands, Norway, Romania, Saudi Arabia, Spain and Switzerland.

Author	
[REDACTED] Clinical Study Manager Swedish Orphan Biovitrum AB (publ) SE-112 76 Stockholm, Sweden [REDACTED] [REDACTED]

---------------	---

Marketing authorization holder(s)

MAH	
Swedish Orphan Biovitrum AB (publ) SE-112 76 Stockholm T: [contact]

------------	--

Table of contents

1	List of abbreviations	6
2	Responsible parties	8
3	Abstract	9

Rationale and background	
Systemic juvenile idiopathic arthritis (SJIA) is the most severe form of juvenile idiopathic arthritis (JIA), characterized predominantly by systemic symptoms, such as high spiking intermittent fever, maculopapular rash, hepatosplenomegaly, lymphadenopathy, serositis, and marked increase in acute-phase reactants, but also chronic arthritis. SJIA is associated with complications, including joint damage, growth impairment, osteoporosis, amyloidosis and the potentially fatal macrophage activation syndrome (MAS). Although its pathogenesis is still not completely understood, it is believed to be of autoinflammatory nature. Laboratory and clinical observations suggest an inappropriate activation of the innate immune system, with hypersecretion of the proinflammatory cytokines interleukin-1 (IL-1) and 6 (IL-6).
 
Kineret® is a recombinant human IL-1 receptor antagonist that has been approved in the EU for treating signs and symptoms of rheumatoid arthritis since 2002 and cryopyrin associated periodic syndromes (CAPS) since 2013. In 2018 the European Commission approved Kineret in adult and pediatric patients for the treatment of Still's disease, including SJIA and adult-onset Still's disease (AOSD), with active systemic features of moderate to high disease activity, or in patients with continued disease activity after treatment with non-steroidal anti-inflammatory drugs (NSAIDs) and/or glucocorticoids.
 
As agreed with EMA, the study is designed to further investigate long-term safety and potential risk for MAS in patients with SJIA treated with Kineret.

Research question and objectives	
The objective of the study is to evaluate and characterize long-term safety of Kineret when used in standard clinical practice to treat patients with SJIA, including MAS as an event of special interest (ESI).
 
The endpoints are:
 
 • The occurrence of non-serious AEs of at least moderate severity and serious AEs (SAEs), including MAS as an ESI. • The duration of Kineret treatment in a real-world setting. • The reasons for Kineret treatment discontinuation.
Study design	An international, non-interventional, single-armed, pharmacovigilance registry study on long-term safety of Kineret utilizing already available data from the ENCePP certified Pharmachild JIA registry.

Study Population	Male and female patients with a diagnosis of SJIA as per the ILAR classification criteria included in the Pharmachild registry study and who were ever treated with Kineret subsequently to SJIA diagnosis.
Variables	The study endpoints are the occurrence of non-serious AEs of at least moderate severity and SAEs, including MAS as an ESI, as well as the duration of the Kineret treatment and reasons for Kineret discontinuation.
Data sources	
The Paediatric Rheumatology International Trials Organisation (PRINTO) is a non-profit, non-governmental, international research network with the goal to foster, facilitate and co-ordinate the development, conduct, analysis, and reporting of multi-centers, international clinical trials and/or outcome standardization studies in children with paediatric rheumatic diseases.
 
The Pharmachild JIA registry, maintained by PRINTO, is a registry collecting data from patients with JIA including patients with SJIA. In the Pharmachild JIA registry 40 countries are participating of which 15 countries have collected data on Kineret treatment.
 
This study includes secondary use of data already available in the Pharmachild JIA registry. The source for the data in the registry is the patients' medical records.

Study size	All patients enrolled in the Pharmachild JIA registry before September 30, 2018 (study end date) meeting the criteria defined for the study population will be included in the study. It is estimated that approximately 300 patients will fulfill these criteria.

Data analysis	
Patient characteristics at baseline will be summarized and presented.
 
The analysis will include calculation of unique incidence rates (with 95% CI) and incidence proportions of each reported term of non-serious AE (moderate and severe) and SAE. A patient may contribute with multiple events of the same AE term. AE specific incidence rates and proportions will be presented overall for the whole study period and also by time windows defined with reference to the first dose of Kineret following a SJIA diagnosis. Analyses of sub-populations with long-term Kineret treatment will enable descriptive comparisons of incidence early in the treatment cycle and incidence resulting from long-term treatment.
 
This study will pay a special interest to the incidence of MAS. Therefore, the time to event since start of Kineret treatment, in this scenario regardless of whether the patient was on Kineret treatment when the event occurred, and the cumulative probability of a first MAS event over time will be analyzed. Trigger events associated with each MAS episodes will be summarized.
 
Summary statistics for the duration of Kineret treatment will be presented overall and by time window.
 
The reasons for Kineret treatment discontinuation will be summarized with number and percentage. Use of other SJIA related medications at baseline and concomitantly with Kineret treatment will be summarized by treatment patterns.

Milestones	
The data extraction from the Pharmachild JIA registry is planned to start in March, 2019 and end in April, 2019. A final study report is planned for October, 2019.

4 Amendments and updates

None.

5 Milestones

This PASS is based on secondary use of data, utilizing already available data from the Pharmachild JIA registry. In the Pharmachild registry data has been collected since 2011. Data collected up until September 30, 2018 will be used in this study. The data extraction from the Pharmachild registry will start as soon as the CSP, SAP and contract with PRINTO have been finalized.

Milestone	Planned date
Start of data collection	March, 2019
End of data collection	April, 2019
Registration in the EU PAS register	March, 2019
Final report of study results	October, 2019

6 Rationale and background

SJIA is an autoinflammatory disease, characterized by chronic arthritis, high spiking intermittent fever, maculopapular rash, hepatosplenomegaly, lymphadenopathy, serositis, and marked increase in acute-phase reactants (1-3). SJIA is associated with complications, including joint damage, growth impairment, osteoporosis, amyloidosis and the potentially fatal MAS (4-8). Laboratory and clinical observations suggest an inappropriate activation of the innate immune system, with hypersecretion of the proinflammatory cytokines interleukin-1 (IL-1) and 6 (IL-6).

Kineret[®] is a human IL-1 receptor antagonist that has been approved in the EU for treating signs and symptoms of rheumatoid arthritis since 2002 and CAPS since 2013. In 2018 the European Commission approved Kineret in adult and pediatric patients for the treatment of Still's disease, including SJIA and AOSD, with active systemic features of moderate to high disease activity, or in patients with continued disease activity after treatment with NSAIDs or glucocorticoids. Kineret can be given as monotherapy or in combination with other anti-inflammatory drugs and DMARDs.

As agreed with EMA, the study is designed to further investigate long-term safety and potential risk for MAS in patients with SJIA treated with Kineret. This non-interventional PASS was included in section III.2-3 of the EU RMP as a category 3 activity.

The protocol for this study is developed in accordance with the EMA guidance for the format and content of the protocol of a non-interventional PASS (9). The study will be registered in the public EU PAS register and on clinicaltrials.gov. The collected safety data will be reported in PSUR and RMP updates where applicable.

7 Research question and objectives

The objective of the study is to evaluate and characterize the long-term safety profile of Kineret treatment when used in standard clinical practice to treat patients with SJIA, including the occurrence of MAS as an ESI.

The endpoints to support the objective for the study are:

- The occurrence of non-serious AEs of at least moderate severity and serious AEs (SAEs), including MAS as an ESI.
- The duration of Kineret treatment in a real-world setting.
- The reasons for Kineret treatment discontinuation.

8 Research methods

8.1 Study design

This is an international, non-interventional, single-armed, pharmacovigilance registry study of long-term safety utilizing already available data from the ENCePP certified Pharmachild JIA registry.

The study endpoints are the occurrence of non-serious AEs of at least moderate severity and SAEs, including MAS as an ESI, as well as the duration of the Kineret treatment and reasons for Kineret discontinuation.

The chosen design is suitable for a study with the primary objective of assessing long-term safety of Kineret when used in patients with SJIA under standard clinical care.

8.2 Setting

Data will be extracted and analyzed for all male and female patients with a diagnosis of SJIA as per the ILAR classification criteria (10, 11) included in the Pharmachild registry and who were ever treated with Kineret subsequently to SJIA diagnosis.

That is, all eligible patients participating in the Pharmachild JIA registry study are included in this study. No specific exclusion criteria will be applied.

No treatment assignment or randomization is applicable.

This study is based on secondary use of data from the Pharmachild registry. The Pharmachild registry was set up in December, 2011. Both retrospective and prospective data has been collected within the registry. The first Kineret treatment, retrospectively collected in the registry, occurred in 2004. Data collected in the registry up until September 30, 2018 will be used in this study. The data extraction from the registry will start in March, 2019 and end in April, 2019.

40 countries participate in the Pharmachild JIA registry. 15 of these countries have collected data from patients meeting the above criteria; Croatia, Denmark, France, Germany, Greece, Hungary, Israel, Italy, Latvia, Netherlands, Norway, Romania, Saudi Arabia, Spain and Switzerland.

8.3 Variables

The study endpoints are the occurrence of non-serious AEs of at least moderate severity and SAEs, including MAS as an ESI, as well as the duration of the Kineret treatment and reasons for Kineret discontinuation.

Management and reporting of AEs are described in Section 10.

In addition, the following will be captured:

- Demographics (sex, ethnicity, country)
- Characteristics at start of Kineret treatment (baseline), i.e. time since disease onset date, time since SJIA diagnosis, co-morbid conditions, history of MAS, global assessment of overall disease activity, age at start of Kineret treatment, SJIA related concomitant medications
- Reason for discontinuation of Kineret treatment.

8.4 Data sources

PRINTO (www.printo.it) is a non-profit, non-governmental, international research network founded by [name] and [name] in 1996 (12). PRINTO initially included 14 European countries (now 88 countries, 640 centers worldwide with 1348 members today), with the goal to foster, facilitate and co-ordinate the development, conduct, analysis, and reporting of international, multi-center, clinical trials and/or outcome standardization studies in children with paediatric rheumatic diseases. PRINTO governing bodies are the advisory council, the national coordinators and the International coordinating center based in Genoa, Italy at the IRCCS G. Gaslini hospital.

The Pharmachild JIA registry, which was set up in December, 2011 with a 3-year grant from EU and is maintained by PRINTO, is a registry collecting data from patients with JIA including patients with SJIA. In the Pharmachild JIA registry 40 countries are participating of which 15 countries have collected data on Kineret treatment: Croatia, Denmark, France, Germany, Greece, Hungary, Israel, Italy, Latvia, Netherlands, Norway, Romania, Saudi Arabia, Spain and Switzerland. The data used in this study will hence be collected from these countries.

The Pharmachild JIA registry study has obtained the ENCePP Study Seal. ENCePP is a collaborative scientific network coordinated by the European Medicines Agency (EMA) and developed in collaboration with European experts in the fields of pharmacoepidemiology and pharmacovigilance. The ENCePP Study Seal means that a study upholds high standards throughout the research process based on the principles of transparency and scientific independence.

As per August 20, 2018 the data source contains both retrospective and prospective data as follows (Table 1).

Table 1

Data type	Number of JIA patients	Number of SJIA patients	Number of SJIA patients treated with Kineret
Only retrospective data	5208	587	212
Retrospective + Prospective data	3508	352	95
Total	8716	939	307

The retrospective data are the data collected from the medical records prior to enrollment in the Pharmachild registry. The prospective data are data collected after enrollment in the registry. For this study retrospective and prospective data will be treated equally.

This study is based on secondary use of data already available in the Pharmachild registry. The source for all data in the registry is the patients' medical records. In the registry both the retrospective and prospective part contain demographics, concomitant medications since onset of disease until last available follow up, AEs that are of at least moderate severity and events of special interest (e.g. MAS). AEs are coded in MedDRA version 21.1. A medical monitor evaluates all reported AEs. This person can raise queries to the centers and request further clarifications.

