9.2 Informed consent

Not applicable. Patients signed an ICF when entering the Pharmachild registry which includes an approval to share data with regulatory authorities (EMA, FDA or national authorities) and pharmaceutical companies, this without collecting additional consent.

In some of the participating countries a signed ICF is not required to collect retrospective data. This is reflected in the Pharmachild registry which contains more retrospective than prospective data as demonstrated in table 1 in section 8.4

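### Pre-enrolment chart data and post-enrolment registry data are pooled as equal, with no presentation by data type and no mention of the issue among the limitations, although 212 of 307 patients have only chart data

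*Protocol*

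**What the plan says.** Protocol Section 8.4 defines the two data types by their position relative to enrolment: "The retrospective data are the data collected from the medical records prior to enrollment in the Pharmachild registry", and "The prospective data are data collected after enrollment in the registry". It then sets the rule: "For this study retrospective and prospective data will be treated equally".

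Table 1 in the same section, dated 20 August 2018, gives counts of JIA patients, SJIA patients and SJIA patients on Kineret, in that order:
- "Only retrospective data 5208 587 212"
- "Retrospective + Prospective data 3508 352 95"
- "Total 8716 939 307"

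Section 8.2 shows how far back the chart data reach: "The first Kineret treatment, retrospectively collected in the registry, occurred in 2004". The registry was set up in December 2011.

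Section 8.7.1 derives each rate from a Poisson model with an intercept and nothing else, overall and in five time windows. Section 8.7.4 adds sets of patients with long continuous treatment, so that early and long-term incidence can be compared descriptively.

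Section 8.9 discusses the uncontrolled design, exposure misclassification and selection into the long-term sets. It also describes a census at each centre before chart review, meant to avoid selection bias. It does not mention differences in event capture by data type, or survival to enrolment. On consent, Section 9.2 says: "In some of the participating countries a signed ICF is not required to collect retrospective data".

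**The concern.** Two mechanisms could make the two kinds of patient-time unequal.

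**Ascertainment.** A non-serious event counts only if it was at least moderate. For pre-enrolment time, its occurrence, onset and intensity must be recovered from notes that were not written for safety collection, and some of these predate the registry by about seven years (2011 − 2004). Prospective follow-up may well record such events more completely. The protocol relies on the registry's safety purpose and detailed exposure recording to limit misclassification, but those features are strongest after enrolment.

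**Survival to enrolment.** The study includes only enrolled patients. Where enrolment needed consent, a patient had to be alive to enter, so earlier time on Kineret could contain no death of that patient but would still count in the denominator.

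The pooling rule governs every rate of non-serious AEs, SAEs and MAS in the study. Under Sections 8.6 and 9.1 the sponsor receives summary output only. If the split is not specified before extraction, the sponsor cannot make it afterwards from patient-level data.

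**Working it through.** **1. Table 1.** The columns add up: 5208 + 3508 = 8716; 587 + 352 = 939; 212 + 95 = 307. The share of Kineret patients with only retrospective data is 212/307 = 69.1%, and the share with any prospective data is 95/307 = 30.9%. These are shares of patients. The protocol gives no patient-time by data type. The retrospective share of patient-time could be above 69%, because the 95 also have pre-enrolment time, or below it if the 95 were followed for much longer.

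**2. Pooled rate.** Let w be the retrospective share of patient-time and s the capture of events in charts relative to prospective follow-up, with prospective capture taken as complete. Then observed/true rate = w·s + (1 − w). Neither w nor s is in the protocol; both are assumed here.

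| w | s = 0.9 | s = 0.8 | s = 0.7 | s = 0.5 |
|---|---|---|---|---|
| 0.69 | 0.93 | 0.86 | 0.79 | 0.66 |
| 0.90 | 0.91 | 0.82 | 0.73 | 0.55 |

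At s = 1 the ratio is 1.00 whatever the mix.

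**3. Early-versus-late contrast, complete set.** With a constant true rate, the apparent late/early ratio is (wL·s + 1 − wL)/(wE·s + 1 − wE), where wE and wL are the retrospective shares in the early and late windows (assumed).

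| wE, wL | s = 0.9 | s = 0.8 | s = 0.7 | s = 0.5 |
|---|---|---|---|---|
| 0.9, 0.5 | 1.04 | 1.10 | 1.16 | 1.36 |
| 0.6, 0.9 | 0.97 | 0.93 | 0.89 | 0.79 |
| equal | 1.00 | 1.00 | 1.00 | 1.00 |

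The contrast is distorted only if capture differs and the mix differs between windows. Nothing in the protocol fixes the sign, because different patients contribute to different windows.

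**4. Early-versus-late contrast, long-term sets.** Here the same patients contribute nearly the full length of each completed window (for the 24-month set: 1-6, 7-12, 13-18 and 19-24 months), apart from short interruptions. By the definitions in Section 8.4, a patient's retrospective time comes before the prospective time. The post-enrolment part of a patient's window therefore cannot shrink from one completed window to the next, and neither can its average over the set. With s below 1, a constant true rate then looks flat or rising. For example, with assumed retrospective shares of 0.8 early and 0.6 late, the apparent ratio is 1.02 at s = 0.9, 1.08 at s = 0.7 and 1.17 at s = 0.5. This does not extend to the final open-ended window, where patients contribute unequal time.

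**5. Survival to enrolment.** Sections 8.5 and 8.7 require enrolment before 30 September 2018. Section 9.2 waives signed consent for retrospective data in some countries, and Section 8.9 requires a census before chart review. Neither says whether a patient who had already died could be included. The size of any effect cannot be calculated.

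**The case against.** The protocol gives reasons to expect similar content. Section 8.4 says that medical records are the source for all registry data, that both parts hold AEs of at least moderate severity and events of special interest, and that a medical monitor evaluates reported AEs and can query centres. This stands as a reason not to assume a large gap. It shows the same fields, though, not the same completeness, and a query about a reported event does not recover one that was never charted.

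A reader might infer that the rates are biased by a known amount. The documents do not support that, because the capture and patient-time figures above are assumptions. A reader might also infer that the late windows of the complete set must look worse. A 50% retrospective share beyond 24 months would need the 95 patients to supply 212/95 = 2.23 times as much time per head as the 212, all of it after enrolment. With equal time per head the late share is at least 69%. Against an assumed 85% early, the ratio is then at most (0.69·0.5 + 0.31)/(0.85·0.5 + 0.15) = 1.14 at s = 0.5 and 1.02 at s = 0.9.

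A third tempting inference is that fatal event rates are biased towards zero. The consent waiver in some countries and the centre census mean that charts of deceased patients may have been included, so this holds only conditionally, where consent was required.

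Finally, the contrasts are descriptive, no hypothesis is tested, and the SAP, which was not available for this review, could add split tables. That lowers the severity. The equal-treatment rule and the gap in Section 8.9 are nevertheless in the protocol itself.

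**Conclusion.** The point stands as a risk of bias that the protocol neither shows nor acknowledges. It fixes equal treatment of two data types when 69.1% of patients have only the retrospective type, and its limitations section is silent on both ascertainment by data type and survival to enrolment.

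If charts under-capture non-serious moderate events, the pooled rates are too low by an unknown amount. The early-versus-late comparison is distorted where the mix differs between windows: in an unknown direction in the complete set, and towards a flat or rising pattern across completed windows in the long-term sets. The survival issue applies where consent was required for retrospective data. All of this assumes that chart capture is no better than prospective capture, which the documents do not establish. Severity: should-fix, with moderate confidence.

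**What to change.** Replace the equal-treatment sentence in Section 8.4 with a rule that incidence rates of non-serious AEs, SAEs and MAS, overall and by time window, are presented for pre-enrolment patient-time, for post-enrolment patient-time, and pooled.

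Add differential ascertainment and survival to enrolment to Section 8.9, and state whether patients who died before enrolment could be included.

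Keep all deaths and fatal MAS in the pooled rate. Show a post-enrolment rate, with delayed entry at enrolment, only as a sensitivity analysis. Using post-enrolment time alone would discard the 212 patients and any deaths validly found in their charts. If no deaths were seen, the one-sided 95% upper bound on the proportion would rise from 1 − 0.05^(1/307) = 1.0% to 1 − 0.05^(1/95) = 3.1%.

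The cost is extra table columns, since the registry already separates the data types, and wide intervals in the prospective column, which rests on at most 95 patients. The change should be settled before extraction, because only summary output reaches the sponsor.
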